In this hierarchical testing structure, each hypothesis is tested at a significance level of 0.05, two-sided. Statistical significance at each step is required in order to test the next hypothesis. If the primary endpoint meets the criteria for statistical significance, then the percent change from baseline to Week 24 in LDL-C will be tested; and so forth.

For the remaining secondary efficacy endpoints and the tertiary efficacy endpoints, a significance level of 0.05 will be used; given the large number of remaining endpoints, the p-values for those endpoints will be considered descriptive.

Percent change from baseline to Week 24 in LDL-C; change from baseline to Weeks 12 and 24 in LDL-C; percent change from baseline to Weeks 12 [REDACTED] in [REDACTED] non-HDL-C, [REDACTED] TC, apoB, and

hs-CRP will each be analyzed using ANCOVA with treatment group and patient type (primary prevention; secondary prevention) as factors and the relevant baseline as a covariate. Baseline for [REDACTED] non-HDL-C, [REDACTED] and TC will be defined as the mean of the lipid values from Week -1 (Visit S3) and predose Day 1/Week 0 (Visit T1). Baseline for apoB and hs-CRP will be defined as the predose Day 1/Week 0 (Visit T1) value. Each ANCOVA will be performed using the FAS, with patients included in their randomized treatment group regardless of the treatment they actually received. Only observed case data will be included in each analysis (no imputation will be performed for missing data). For each lipid parameter and analysis time point, the LSM and SE will be provided for both treatment groups, along with the placebo-corrected LSM, its 95% CI and associated p-value.

For all continuous efficacy endpoints (percent change from baseline in LDL-C, [REDACTED] non-HDL-C, TC, [REDACTED] apoB, and hs-CRP; change from baseline in LDL-C; to Weeks 12 and 24, as appropriate), the ANCOVA assumption of normality will be assessed. If non-normality of the data is found at any time point for any parameter, either the data will be transformed so that it is normally distributed or a nonparametric test will be used instead of the planned ANCOVA.

Additional Post-randomization Adjunctive Triglyceride-lowering Therapy:

The number and percent of patients in each treatment group requiring additional (post-randomization) TG-lowering therapy will be summarized. The medications will be summarized by treatment group.

Safety Analyses

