5.2.2. Secondary Endpoints

1. Percent change from baseline to Week 24 in LDL-C
2. Percent change from baseline to Week 12 in non-HDL-C, TC, apoB, and hs-CRP
3. Absolute change from baseline to Weeks 12 and 24 in LDL-C

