Each ANCOVA will be performed using the FAS, with patients included in their randomized treatment group regardless of the treatment they actually received. Same imputation method described for the primary endpoint will be used for those secondary endpoints included in the step-down procedure, while only observed data analysis will be used for other secondary and tertiary endpoints. For each lipid parameter and analysis time point, the LSM and SE will be provided for both treatment groups, along with the placebo-corrected LSM, its 95% CI and associated p-value.

The ANCOVA assumption of normality will be assessed. If severe non-normality of the data is found at any time point for any parameter, either the data will be transformed so that it is normally distributed or a nonparametric test will be considered instead of the planned ANCOVA.

Finally, the number and percent of patients in each treatment group requiring additional (post-randomization) TG-lowering therapy will be summarized. The medications will be summarized by treatment group.

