Each ANCOVA will be performed using the FAS, with patients included in their randomized treatment group regardless of the treatment they actually received. ***Same imputation method described for the primary endpoint will be used for those secondary endpoints included in the step-down procedure, while only observed data analysis will be used for other secondary and tertiary endpoints. Only observed case data will be included in each analysis (no imputation will be performed for missing data).*** For each lipid parameter and analysis time point, the LSM and

SE will be provided for both treatment groups, along with the placebo-corrected LSM, its 95% CI and associated p-value.

~~For all continuous efficacy endpoints (percent change from baseline in LDL-C, HDL-C, non-HDL-C, apoB, and hs-CRP; change from baseline in LDL-C; to Week 12 and 24, as appropriate),~~ The ANCOVA assumption of normality will be assessed. If *severe* non-normality of the data is found at any time point for any parameter, either the data will be transformed so that it is normally distributed or a nonparametric test will be ~~used~~ *considered* instead of the planned ANCOVA.

Finally, the number and percent of patients in each treatment group requiring additional (post-randomization) TG-lowering therapy will be summarized. The medications will be summarized by treatment group.

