**18.1.3. MISSING DATA METHODS FOR PRIMARY EFFICACY VARIABLE**

For the primary endpoint of percent change from baseline to Week 12 in LDL-C values, a pattern mixture model (PMM) will be used to specify different imputation strategies depending on whether the patient is still on study treatment. Patients with missing lipid data at Week 12 who are no longer taking study treatment (defined by date of last dose of study medication is < Week 12 lab assessment date -7) can be assumed to no longer be benefitting from study medication, and their missing value(s) can be assumed to be similar to those in placebo group who remained on study and have data. To account for uncertainty, missing values will be imputed using multiple imputation via a regression based model including stratification and baseline data from placebo subjects only. In this imputation model, treatment group will not be included as a factor.

Patients with missing lipid data at Week 12 who are still taking study treatment (date of last dose of study medication is ≥ Week 12 lab assessment date -7) can be assumed to continue to benefit from study medication, and their missing value(s) can be assumed to be similar to those who remain on study treatment and have data and as a result, lipid values will be imputed based on the observed values in their randomized treatment group at Week 12. To account for uncertainty, missing values will be imputed using multiple imputation via a regression based model including treatment, stratification and baseline value.

Imputed datasets will be analyzed using the same ANCOVA model with treatment and stratification as factors and baseline LDL-C as a covariate described in [section 18.1.2](#). Approximately 200 imputed datasets will be created, with results from the analysis of each imputed dataset combined using Rubin’s method. The least squares mean (LSM) and standard error (SE) will be provided for both treatment groups, along with the placebo-corrected LSM, its 95% confidence interval (CI) and associated p-value. To account for possibility of unequal variances between the groups, the ANCOVA model will be implemented within mixed model framework where <repeated/group=> option will be used to allow separate estimation of residual variance between the groups.

Further information on the multiple imputation method is presented in [Appendix 4](#).

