**18.2.2. OTHER SECONDARY EFFICACY VARIABLES & DERIVATIONS**

Other secondary efficacy endpoints are:

- Change from baseline to Week 12 in LDL-C
- Change from baseline to Week 24 in LDL-C.

The absolute change in LDL-C at week 12, 24 will be summarized using descriptive statistics.

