**18.2.4. SUBGROUP ANALYSIS OF EFFICACY VARIABLE**

The primary endpoint for LDL-C will be analysed within subgroups below using the same analysis method previously described. The treatment and subgroup interaction will be examined by including the interaction term in the ANCOVA model for the overall population first. No imputation will be performed on missing data for subgroup analyses. In case the number of subjects within a subgroup is too small, e.g. less than 5% of the overall population, the analyses may not be performed or the subgroup levels may be combined. Forest plots for the primary efficacy variable will also be presented.

- CVD risk category (primary prevention; secondary prevention)
- Baseline LDL category (<130mg/dL,  $\geq$ 130 mg/dL and < 160 mg/dL,  $\geq$ 160mg/dL )
- History of diabetes (yes vs.no)
- Age (< 65 yrs. vs.  $\geq$ 65 yrs. and <75 yrs vs.  $\geq$ 75 yrs)
- Race (White vs. Non-White))
- Gender (male vs. female)
- BMI category (< 25 vs. 25 - < 30 vs.  $\geq$  30 kg/ m2)
- Background lipid modifying therapy (statin vs. non-statin vs. none)

[Redacted]

Version Number: 1.7  
 Version Date: 21Mar2018

[Redacted]

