**APPENDIX 4. DETAILS OF MULTIPLE IMPUTATION METHOD**

Missing Week 12 values will be imputed based on baseline values. The following table details the possible cohorts and which cohorts will be used for imputation. Missing Week 24 values will be imputed in the same way.

	Treatment	Week 12 Value	On Treatment at Week 12	Imputation Cohort(s)
1	Placebo	Missing	Yes	Cohort 5: Placebo patients with non-missing Week 12
2	BA	Missing	Yes	Cohorts 6 and 8 BA patients with non-missing Week 12
3	placebo	Missing	No	Cohort 5: Placebo patients with non-missing Week 12
4	BA	Missing	No	Cohorts 5 and 7 Placebo patients with non-missing Week 12 and not on treatment
5	placebo	Non-missing	Yes	
6	BA	Non-missing	Yes	
7	placebo	Non-missing	No	
8	BA	Non-missing	No	

Imputation code for Cohorts 1-3.

```
proc mi;
where cohort in(1,2,3,5,6,8);
class trt01pn strata;
monotone regression;
var trt01pn strata base aval;
run;
```

Imputation code for Cohort 4.

```
proc mi;
where cohort in(4,5,7);
class strata;
monotone regression;
var base strata aval;
run;
```

[figure not shown]
Version Number: 1.7  
 Version Date: 21Mar2018

Two hundred imputed datasets will be created, with results from the analysis of each imputed dataset (ANCOVA) combined using Rubin’s method.

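### Absolute LDL-C change is left unimputed while percent change from the same LDL-C values is imputed, so the mg/dL result can look larger than the plan's own missing-data assumption allows

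*Protocol*

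**What the plan says.** **The endpoint.** Protocol 5.2.2 lists "Absolute change from baseline to Weeks 12 and 24 in LDL-C" as a secondary endpoint. SAP 18.2.2 classes it as an other secondary endpoint, and it is not in the step-down sequence of SAP 7.5.

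**Its missing-data rule.** Protocol 11.6 splits the endpoints in two. Those in the step-down sequence are imputed as the primary endpoint is. The rest, absolute change among them, are not: "while only observed data analysis will be used for other secondary and tertiary endpoints". SAP 18.2.2 says "The absolute change in LDL-C at week 12, 24 will be summarized using descriptive statistics" and gives neither a model nor a rule for missing values. SAP 7.4 sends the reader to 18.1.2 for missing efficacy data, but that section has no such rule. The imputation is in 18.1.3 for the primary endpoint, and 18.2.1 extends it to the key secondary endpoints only.

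**Its analysis.** Read alone, protocol 11.6 implies an ANCOVA for absolute change, with least squares means, a confidence interval and a p-value. The SAP has descriptive statistics only. Under protocol 11.1 the SAP prevails.

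**Percent change from the same values.** For patients no longer on drug whose Week 12 value is missing, SAP 18.1.3 says "their missing value(s) can be assumed to be similar to those in placebo group who remained on study and have data". Missing values in patients still on drug are imputed from their own arm. About 200 datasets are created, and Appendix 4 adds: "Missing Week 24 values will be imputed in the same way".

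**The concern.** Percent and absolute change at a given week use one baseline and one LDL-C value. For percent change, the plan assumes that a bempedoic acid patient who has stopped drug and has no value no longer benefits. For absolute change the same patient is left out, which in a comparison of arms amounts to assuming a response like that of the patients who were measured. The plan gives no reason for treating one measurement in two ways.

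At stake is the mg/dL reduction, a figure that readers will set beside the headline percent reduction. Under the plan's own assumption, leaving these patients out can move it only in the drug's favour.

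**Working it through.** **Inputs from the documents.** 200 bempedoic acid and 100 placebo patients (protocol 6.2); 200 imputed datasets; the imputation cohorts of SAP Appendix 4. The public text gives no effect size, standard deviation or dropout rate, so there is no stated figure to reproduce.

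**Assumed inputs.** *d*, the mean placebo-corrected absolute LDL-C reduction among patients with a value: 20 to 40 mg/dL. *f*, the share of bempedoic acid patients both off drug and missing: 0 to 10%.

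**Formula.**
- Observed cases: effect = d.
- Plan's imputation: off-drug missing patients on bempedoic acid contribute a placebo-like value, so effect = (1 − f) × d + f × 0 = d(1 − f).
- Gap = d − d(1 − f) = d × f. Relative excess = 1/(1 − f) − 1.

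Three groups do not contribute to the gap. Patients missing while on drug are imputed from their own arm. Missing placebo patients are imputed from placebo. Patients off drug but measured enter both analyses unchanged.

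| f | Patients of 200 | Gap, d = 20 | Gap, d = 30 | Gap, d = 40 | Relative excess |
|---|---|---|---|---|---|
| 0 | 0 | 0 | 0 | 0 | 0% |
| 1% | 2 | 0.2 | 0.3 | 0.4 | 1.0% |
| 2% | 4 | 0.4 | 0.6 | 0.8 | 2.0% |
| 5% | 10 | 1.0 | 1.5 | 2.0 | 5.3% |
| 10% | 20 | 2.0 | 3.0 | 4.0 | 11.1% |

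(Gaps in mg/dL.)

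**Simulation check.** The Appendix 4 imputation was run with ANCOVA on absolute change and Rubin's rules: 150 trials per row, 50 imputations each. Assumptions: baseline 155 mg/dL (SD 38), effect −22 percentage points, percent-change SD 20, residual variance pooled across arms.

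| Off drug and missing (f) | On drug, missing | Off drug, measured | Observed | Imputed | Gap |
|---|---|---|---|---|---|
| 0 | 5% | 0 | −33.93 | −33.93 | 0.0 |
| 0 | 5% | 10% | −30.27 | −30.27 | 0.0 |
| 2% | 2% | 5% | −31.75 | −31.11 | 0.63 |
| 5% | 2% | 5% | −32.22 | −30.62 | 1.60 |
| 10% | 2% | 5% | −31.93 | −28.74 | 3.19 |

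These agree with d × f; for example, 31.93 × 0.10 = 3.19. The standard error of the effect was about 4.1 to 4.4 mg/dL, so every gap is below one standard error.

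**Feasibility.** Protocol 11.5 speaks of imputing LDL-C values, and the Appendix 4 code imputes `aval` with `base` in the model. If `aval` is the LDL-C value, absolute change is `aval` minus `base`. If it is the percent change, absolute change is `base` × `aval`/100. No new imputation is needed either way.

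**The case against.** **The governing plan schedules no formal absolute effect.** This is correct. Under SAP 18.2.2 there is no model, confidence interval or test for absolute change, and protocol 11.6 makes p-values outside the hierarchy descriptive. That limits the consequence. It does not remove the inconsistency, because arm means that omit these patients carry the same gap when one is subtracted from the other.

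**A reader might infer that the absolute effect is overstated as a matter of fact.** The documents do not support that. A gap needs bempedoic acid patients who are both off drug and missing, and no such rate is given. Protocol 8.4 asks patients who stop drug to keep attending, with fasting lipids, which should keep f down. The gap is also measured against the plan's placebo-based assumption, which is itself an assumption.

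**A reader might infer a conflict with the full analysis set.** There is none. That set fixes which patients are eligible and in which arm they count, and observed data can be analysed within it, as SAP 18.2.3.3 does for the on-treatment analysis.

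**A reader might infer that the mg/dL figure has no matching percent change.** SAP 18.2.3.4 plans an observed-case analysis of the primary and key secondary endpoints, so a like-for-like companion exists. It is a sensitivity analysis there, whereas for absolute change observed cases are the only basis.

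**A reader might extend the point to subgroups**, where SAP 18.2.4 says "No imputation will be performed on missing data for subgroup analyses". That does not follow. The Appendix 4 model holds only treatment, stratum and baseline. It has no treatment-by-subgroup term and omits most of the subgroup variables, so imputing from it would pull most interactions toward zero. Observed cases are a defensible choice there, and the observed-case overall analysis is the right comparator.

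**Conclusion.** The inconsistency stands: one LDL-C measurement follows two missing-data rules, and the governing SAP gives no rule at all for absolute change. The consequence is conditional and modest. If f is above zero and the drug lowers LDL-C, the observed absolute difference is expected to exceed the estimate under the plan's own imputation by d × f: from 0.4 mg/dL (d = 20, f = 2%) to 4.0 mg/dL (d = 40, f = 10%) over the assumed range. Both d and f are assumptions.

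The primary result, error control and the step-down sequence are untouched. The change is still worth making, because the possible error runs one way and the remedy uses datasets that the plan already creates.

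**What to change.** In protocol 11.6 and SAP 18.2.2, derive absolute LDL-C change at Weeks 12 and 24 from the same 200 imputed LDL-C datasets used for percent change, analyse it with the ANCOVA of SAP 18.1.2, and combine by Rubin's method. Keep the observed-case summary as supportive, labelled as such and shown beside the observed-case percent change. The p-value stays descriptive. Leave the subgroup analyses in SAP 18.2.4 as they are.

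Two wording points belong in the same edit. SAP 7.4 should point to 18.1.3. The protocol synopsis should be aligned with 11.6, since it still applies observed cases to all secondary endpoints, including percent change at Week 24.

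The cost is wording in both documents, one derived variable per imputed dataset, and possibly a slightly less favourable mg/dL figure.

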11.7 Safety Analysis

~~No statistical analyses will be performed on any of the safety data in this study.~~

The summarization of AEs will include TEAEs, defined as any unfavorable and unintended sign, symptom, or disease temporally associated with the use of the investigational product, whether or not related to the product. TEAEs and SAEs will be summarized by SOC, severity, and relationship to study drug for each treatment group. These AE summaries will include cumulative incidence (percent of patients experiencing the AE) and patient-year adjusted incidence rates. If appropriate, absolute and relative risk differences will be calculated using both cumulative incidence and incidence rates. Deaths, withdrawal from study treatment due to AEs, and withdrawal from the study due to AEs will each be summarized by treatment group.

CHANGE 32 PHARMACOKINETIC SAMPLE REVISION

Location:

Section 2, Synopsis; Section 11.8, Pharmacokinetics

Original Text:

Four plasma PK samples for analysis will be collected. Plasma concentrations of bempedoic acid and optionally, one or more of its metabolites, will be determined in patients who are receiving bempedoic acid. All patients, site personnel, and study personnel will remain blinded to treatment assignment throughout the duration of the study. Personnel performing the bioanalytical analysis of bempedoic acid concentrations will be unblinded in order to assay the appropriate samples during the study. Plasma concentrations of bempedoic acid and any measured metabolite will be included in the listings, but population PK analysis will be reported separately will be descriptive by time point.

New Text:

~~Four~~ *Three* plasma PK samples for analysis will be collected. Plasma concentrations of bempedoic acid and optionally, one or more of its metabolites, will be determined in patients who are receiving bempedoic acid. All patients, site personnel, and study personnel will remain blinded to treatment assignment throughout the duration of the study. Personnel performing the bioanalytical analysis of bempedoic acid concentrations will be unblinded in order to assay the

appropriate samples during the study. Plasma concentrations of bempedoic acid and any measured metabolite will be included in the listings, but population PK analysis will be reported separately will be descriptive by time point.

CHANGE 33 INFORMED CONSENT REVISION

Location:

Section 14.3, Written Informed Consent

Original Text:

The patient's signed and dated informed consent must be obtained before conducting any study procedures.

A separate informed consent will be obtained for collecting the genetic blood sample.

The Principal Investigator(s) must maintain the original, signed ICD. A copy of the signed ICD must be given to the patient.

New Text:

The patient's signed and dated informed consent must be obtained before conducting any study procedures.

~~A separate informed consent will be obtained for collecting the genetic blood sample.~~

The Principal Investigator(s) must maintain the original, signed ICD. A copy of the signed ICD must be given to the patient.

CHANGE 34 CASE REPORT FORM COLLECTION REVISION

Location:

Section 15.3, Case Report Forms and Study Records

Original Text:

It is essential that all dates appearing on the Sponsor's patient data collection forms for laboratory tests, cultures, etc, be the dates on which the specimens were obtained or the procedures performed. The eCRFs will be electronically signed by the Investigator and dated as verification of the accuracy of the recorded data. All data collection forms should be completed within 48 hours following the evaluation.

New Text:

It is essential that all dates appearing on the Sponsor's patient data collection forms for laboratory tests, cultures, etc, be the dates on which the specimens were obtained or the procedures performed. The eCRFs will be electronically signed by the Investigator and dated as verification of the accuracy of the recorded data. All data collection forms should be completed ***a timely manner according to the CRF completion guidelines.***~~within 48 hours following the evaluation.~~

CHANGE 35 STUDY ADMINISTRATIVE STRUCTURE REVISION

Location:

[figure not shown]
Section 16.2, Study Administrative Structure

Original Text:

[figure not shown]
Fill/Finish Manufacturing:

And

[figure not shown]
Secondary Packaging/Depot for Clinical Site Drug Shipments:

[figure not shown]
New Text:

Investigational medicinal product supply chain details can be found in the pharmacy manual.

[figure not shown]
~~Fill/Finish Manufacturing:~~

~~And~~

~~Secondary Packaging/Depot for Clinical Site Drug Shipments:~~

CHANGE 36 SCHEDULE OF EVENTS REVISIONS

Location:

Appendix 1, Schedule of Events

Original Text:

APPENDIX 1. SCHEDULE OF ASSESSMENTS

Visit	S1 ^{1,2}	S2	S3	T1	T2	T3/phone	T4	T5/EOS ³
Week	Wk -5	Wk -4	Wk -1	Wk 0	Wk 4	Wk 8	Wk 12	Wk 24
Procedure	Day -63 to -29	Day -28±3	Day -7±3	Day 1	Day 29±3	Day 57±3	Day 85±3	Day 169±7
Informed Consent	X							
Enrollment Criteria	X							
Demographics	X							
Medical History	X							
Statin Intolerance Status Determination	X							
Concomitant Medications	X	X	X	X	X	X	X	X
Adverse Event Recording		X	X	X	X	X	X	X
Physical Exam		X						X
Weight ⁴	X			X			X	X
Height/BMI	X							
12-Lead ECG ⁵			X					X
Vital Signs ⁶	X	X	X	X	X		X	X
Serology ⁷	X							
Serum Pregnancy/FSH ⁸	X							
Urine Pregnancy ⁹				X				
TSH	X							
Clinical Safety Labs ¹⁰	X		X	X	X		X	X
Basic Fasting Lipids ¹¹	X		X	X	X		X	X
HbA _{1c}	X			X			X	X
10-mL reserve sample				X				X
PK Sample				X	X		X	X
Pharmacogenomics Sample (optional)				X				
apoB				X			X	X
hs-CRP				X			X	X
Diet and exercise counseling ¹²	X	X	X	X	X	X	X	
Establish Patient Eligibility		X		X				
Randomization				X				
IWRS Contact ¹²	X	X		X			X	X
Single-blind Drug Dispensing		X						
Double-blind Drug Dispensing				X			X	
Drug Return/Compliance			X	X	X		X	X

NOTE: For patients who withdraw from study drug treatment, but consent to be followed for safety assessments and return to clinic for these visits, the visits will occur according to the protocol schedule. Safety assessments should include clinical safety and basic lipid laboratories (except for apoB and hs-CRP), adverse events (AEs), physical examination (PE), vital signs, and electrocardiograms (ECGs). For patients who withdraw from study drug treatment, but consent to be followed for safety assessments by phone, the telephone contacts will occur according to the protocol schedule with information regarding current health status and to collect information on AEs (eg, recent procedures, hospitalizations, and if the patient has died, the cause of death). If a patient does not provide consent to be followed for safety assessments per the protocol (either by returning to clinic or by phone), Visit T5 will be considered the End of Study (EOS)/Early Withdrawal from study and no further visits will be scheduled.

- ¹ An optional basic fasting (minimum of 10 hours) lipid MAY be completed at Visit S2 (prior to starting single-blind medication) if patient fails to meet lipid entry criterion at Visit S1. If this optional basic fasting lipid is completed, the mean of the first value and the repeat value will be used to determine eligibility.
- ² A recheck of blood pressure may be completed at Visit S2 if the patient's DBP and/or SBP meet the exclusion criteria levels. Patients may randomize after blood pressure medications have been adjusted, the patients have been on stable doses of blood pressure medications for at least 2 weeks, and the repeat blood pressure values (diastolic blood pressure [DBP] and/or systolic blood pressure [SBP]) do not meet exclusionary values. Repeat labs may be completed at Visit S2 to determine eligibility if the patient's estimated glomerular filtration rate (eGFR), alanine aminotransferase (ALT), aspartate aminotransferase (AST) or other labs meet exclusion criteria levels. If this optional lab is completed, the repeated value will be used to determine eligibility.
- ³ All procedures will be completed for all patients at either EOS if completing the study or early withdrawal.
- ⁴ Body weight will be measured while fasting, using consistent scales, after voiding, and without shoes and outerwear (eg, coats).
- ⁵ Single 12-lead ECG will be performed prior to any blood sample collection.
- ⁶ Vital signs will include DBP, SBP, heart rate (HR) and will be collected prior to any blood sample collection. Patient will rest for 5 minutes prior to assessments.
- ⁷ Serology for HBsAg, HCV-ABVivi.
- ⁸ Pregnancy test completed in women of child-bearing potential only. FSH in naturally postmenopausal women ≥ 1 year without menses and < 55 years;
- ⁹ Urine pregnancy test completed in women of child-bearing potential only just prior to randomization.
- ¹⁰ Clinical safety labs include hematology, blood chemistry, and urinalysis at all visits. A coagulation panel will be completed for all patients at Week -5 (Visit S1). A coagulation panel will be completed only for patients on anti-coagulant therapy at Day 1 (Visit T1) and 3 to 5 days later. Please refer to laboratory manual for detailed schedule of tests.
- ¹¹ Basic fasting (minimum of 10 hours) lipids include total cholesterol, calculated low-density lipoprotein cholesterol (LDL-C), high-density lipoprotein cholesterol (HDL-C), non-HDL-C, and triglycerides. Repeat within 1 week if exceed protocol-specified criteria.
- ¹² Diet and exercise counseling per local and/or regional guidelines for the management of hyperlipidemia.
- ¹³ Interactive web response system (IWRS) contact at either an early withdrawal or an EOS visit to register study discontinuation visit date.

New Text:

